8.1 Intent-to-Treat (ITT) Set

The ITT Set will include all randomized subjects. Summaries and analyses of the ITT Set will classify subjects according to the treatment to which they were randomized.

8.2 Modified Intent-to-Treat (mITT) Set

The mITT Set will include all randomized subjects with at least one eye in which the IOL touches the eye with a study lens. Summaries and analyses of the mITT Set will classify subjects according to the treatment to which they were randomized. Randomized subjects who will be excluded from this set will be identified prior to database lock and unmasking.

8.3 Modified Safety Set

The Modified Safety set will include all subjects with at least one eye in which the IOL touches the eye with a study lens. Summaries and analyses of the Modified Safety Set will classify subjects according to the treatment received.

8.4 Per Protocol (PP) Set

The Per-Protocol (PP) Set will include all bilaterally implanted subjects without major protocol deviations. The PP set will summarize eyes/subjects as treated.

A major protocol deviation will be defined as a deviation that is expected to impact the key safety or effectiveness outcomes, or which has an effect on subject safety. The major protocol deviations will be determined prior to treatment unmasking.

8.5 Best Case Set

The purpose of the Best Case Set is to evaluate BCDVA as a part of the primary safety analysis as described in ISO 11979-7. The Best Case Set will include subjects with all the following characteristics:

- No clinically significant pre-operative ocular pathology in the first eye, including any of the following present prior to the operative visit
 - Pseudoexfoliation
 - Glaucoma
 - Uveitis
 - Retinal detachment
 - Diabetic retinopathy
 - Macular degeneration
 - Amblyopia
 - Other pre-operative pathologies that are likely to affect central acuity
- No macular degeneration detected at any time in the first eye
- No previous surgery for the correction of refractive errors in the first eye

Prior to treatment unmasking, other criteria may be added. The Best Case Set will summarize eyes/subjects as treated.

9 General Statistical Considerations

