3.3.5 Primary Effectiveness Endpoints

The statistical success of the trial will depend on the statistical success of all three primary effectiveness endpoints.

First Primary Effectiveness Endpoint

For the first primary effectiveness endpoint, photopic monocular logMAR BCDVA in first eyes at Post-Operative Visit 4 (Day 120 to 180 after second eye IOL implantation), there are three hypotheses to be tested. The Test IOL must be successful in all three hypothesis tests to achieve success in this endpoint.

The first null (H_0) and alternative (H_1) hypotheses are as follows:

$$H_0: \mu_T - \mu_C \geq 0.10$$
$$H_1: \mu_T - \mu_C < 0.10$$

Where:

- μ_T = the mean logMAR BCDVA of the Test (trifocal) group
- μ_C = the mean logMAR BCDVA of the Control (monofocal) group
- 0.10 is the non-inferiority margin

If the null hypothesis is rejected, then it will be concluded that the Test IOL is statistically successful in this evaluation.

The second null (H_0) and alternative (H_1) hypotheses are as follows.

$$H_0: \pi_T \geq 0.925$$

$$H_1: \pi_T < 0.925$$

Where π_T = the proportion of mITT Set Test (trifocal) group eyes with BCDVA 20/40 or better. The ISO standard specifies a nontraditional evaluation of these hypotheses, with failure to reject the null hypothesis indicating success. If the null hypothesis is not rejected, then it will be concluded that the Test IOL is statistically successful in this evaluation.

The third null (H_0) and alternative (H_1) hypotheses are as follows.

$$H_0: \pi_T \geq 0.967$$
$$H_1: \pi_T < 0.967$$

Where π_T = the proportion of Best Case Set Test (trifocal) group eyes with BCDVA 20/40 or better. The ISO standard specifies a nontraditional evaluation of these hypotheses, with failure to reject the null hypothesis indicating success. If the null hypothesis is not rejected, then it will be concluded that the Test IOL is statistically successful in this evaluation.

Second Primary Effectiveness Endpoint

For the second primary effectiveness endpoint, photopic monocular logMAR DCNVA in first eyes at Post-Operative Visit 4 (Day 120 to 180 after second eye IOL implantation), the null (H_0) and alternative (H_1) hypotheses are as follows:

$$H_0: \mu_T = \mu_C$$
$$H_1: \mu_T \neq \mu_C$$

Where:

- μ_T = the mean logMAR DCNVA of the Test (trifocal) group
- μ_C = the mean logMAR DCNVA of the Control (monofocal) group

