13.3.1 Photopic Monocular BCDVA

Photopic monocular BCDVA (logMAR) in first eyes at Post-Operative Visit 4 (Day 120 to 180 after second eye IOL implantation) will be summarized using continuous summary statistics by treatment group. Imputation of missing data is not conservative in non-inferiority testing. Therefore, missing data will not be imputed for the BCDVA non-inferiority test. An analysis of covariance (ANCOVA) model will be constructed with BCDVA as the dependent variable and treatment and site as fixed factors. The treatment effect (least squares [LS] mean for Test group IOL minus LS mean for Control group IOL) will be estimated in addition to a two-sided 90% CI. If the upper confidence limit (equivalent to a one-sided upper 95% confidence limit for the treatment effect) is less than 0.1, then the Test lens will be statistically non-inferior to the control lens. The summary and analysis will be performed for both ITT and mITT Sets.

The previous continuous summary statistics will also be provided for the PP Set. However, non-inferiority will not be evaluated with the PP Set, and statistical success will not depend upon the results of the PP analysis.

The BCDVA at Post-Operative Visit 4 (Day 120 to 180 after second eye IOL implantation) for the Test group will be summarized categorically (20/20 or better, 20/25 or better, 20/32 or better, 20/40 or better, and worse than 20/40) for the ITT, mITT, and Best Case Sets. Two-sided exact binomial 90% CIs around the proportions of eyes 20/40 or better will be presented. Categorical summaries will use whole line binning as shown in Table 4.

Table 4. logMAR to Snellen Conversion Table

logMAR Value	Cumulative Snellen Category
≤ 0.00	20/20 or better
≤ 0.10	20/25 or better
≤ 0.20	20/32 or better
≤ 0.30	20/40 or better
> 0.30	Worse than 20/40

For the analyses of the ITT, mITT, and Best Case Sets, one-sided exact binomial tests comparing the proportion of Multifocal IOL eyes with BCDVA 20/40 or better to the relevant control rate (92.5% for all eyes in ITT and mITT Sets and 96.7% for Best Case Set eyes) will be performed, and p-values will be presented. If the p-value is less than or equal to 0.05, then the null hypothesis will be rejected. Similar analysis will be performed for first eyes and second eyes as supportive analysis.

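### SAP 8.5 lets Best Case criteria be added until treatment unmasking, but the set feeds a required Test-arm-only test against 96.7% that arm masking does not protect

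*SAP*

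**What the plan says.** SAP 8.5 defines the Best Case Set by a list of pre-operative pathologies in the first eye, absence of macular degeneration at any time, and no earlier refractive surgery. The list ends with a judgement item, "Other pre-operative pathologies that are likely to affect central acuity". The section then adds: "Prior to treatment unmasking, other criteria may be added".

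Protocol 13.4.5 gives the same list, including the judgement item, but not that last sentence. SAP section 16, which records changes from the protocol, does not mention it. For contrast, SAP 8.2 requires mITT exclusions to be identified before both database lock and unmasking.

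The set is used in the third BCDVA hypothesis (SAP 3.3.5), whose parameter is "the proportion of Best Case Set Test (trifocal) group eyes with BCDVA 20/40 or better". SAP 13.3.1 specifies "one-sided exact binomial tests comparing the proportion of Multifocal IOL eyes with BCDVA 20/40 or better to the relevant control rate", with reference rates of "92.5% for all eyes in ITT and mITT Sets and 96.7% for Best Case Set eyes". The decision rule is "If the p-value is less than or equal to 0.05, then the null hypothesis will be rejected". SAP 3.3.5 describes the evaluation as nontraditional, "with failure to reject the null hypothesis indicating success", and adds: "The Test IOL must be successful in all three hypothesis tests to achieve success in this endpoint". Trial success in turn needs all three primary effectiveness endpoints.

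**The concern.** Masking to treatment protects a comparison between arms, because an exclusion rule chosen without knowing the arm cannot be aimed at one side. The 96.7% test has no Control term. Defining out an eye worse than 20/40 raises the Test rate if it is a Test eye and leaves it unchanged if it is a Control eye. With 2:1 allocation about two thirds of all eyes are Test eyes. Since failing to reject is success, removing poor-acuity eyes never works against the lens.

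The clause sets a latest date, treatment unmasking, by which time Visit 4 acuities can already be in the database. Nothing in SAP 8.5 requires added criteria to be baseline characteristics, to be fixed before Visit 4 acuity is available or before database lock, or to be chosen by people who have not seen acuity. A criterion chosen with knowledge of the results would therefore comply with the SAP and could settle a test on which the first primary effectiveness endpoint depends.

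**Working it through.** **Inputs from the documents.** Reference rate 0.967, so the reference failure rate is 1 − 0.967 = 0.033. One-sided exact binomial test, reject at p ≤ 0.05 (SAP 13.3.1). About 300 completed Test subjects (SAP 6.4 and 6.7).

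**Assumptions.** The documents do not give the size of the Best Case Set. I use 300 Test eyes and show 240 to 334. The true rates of 94%, 95% and 96% are also assumed.

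**The plan's own figure.** Enrolment: 300/(1 − 0.1) = 333.3, rounded up to 334, as stated. No power or error rate is stated for the 96.7% test.

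**Pass limit.** With f eyes worse than 20/40 among n, p = P(X ≥ f), where X ~ Binomial(n, 0.033). The test passes if p > 0.05.

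| Test eyes n | Most failing eyes that pass | p at that number | p with one more |
|---|---|---|---|
| 240 | 13 | 0.057 | 0.030 |
| 270 | 14 | 0.066 | 0.036 |
| 300 | 15 | 0.075 | 0.043 |
| 334 | 17 | 0.054 | 0.030 |

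**Effect on a given result (n = 300).**
- 16 failing, p = 0.043, fails. Remove 1 failing eye: 15 of 299, p = 0.073, passes.
- 18 failing (94.0% successful), p = 0.012, fails. Remove 3 failing eyes: 15 of 297, p = 0.070, passes.

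**Chance of passing, upper bound.** Let F ~ Binomial(300, 1 − true rate) be the number of failing eyes. Remove r failing Test eyes and no passing eyes, then apply the test to F − r failures among 300 − r eyes. The limit stays at 15 for r = 0 to 3, so the chance is P(F ≤ 15 + r).

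| True rate | r = 0 | r = 1 | r = 2 | r = 3 |
|---|---|---|---|---|
| 96% | 85% | 90% | 94% | 97% |
| 95% | 57% | 67% | 75% | 82.5% |
| 94% | 28% | 37% | 47% | 56% |

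At a true rate of exactly 96.7% the chance with fixed criteria is already 96%.

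**When passing eyes go too.** A criterion removes every eye that meets it. Start from 16 of 300 and remove 1 failing and m passing Test eyes, leaving 15 failing of 299 − m:
- m = 14: 15 of 285, p = 0.053, passes.
- m = 16: 15 of 283, p = 0.0505, passes.
- m = 17: 15 of 282, p = 0.049, still fails.

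With 1 failing and 20 passing eyes removed, 279 remain and the limit drops to 14. Passing then needs F − 1 ≤ 14, that is F ≤ 15, the same as with no exclusion. At a 95% true rate the chance stays at 57%.

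**Would the other binomial test catch it?** Against 92.5% (failure rate 0.075) with 300 eyes, 30 failing eyes still pass (p = 0.067). A lens with 16 to 20 failing eyes passes that test easily, so it does not back up the 96.7% test.

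**The case against.** Several points on the other side stand.

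- The clause allows criteria to be added; it does not allow chosen eyes to be deleted. A reader might infer from the pass limit that any single exclusion can turn failure into success. That needs a Test eye, a result at the limit, and a criterion that takes few passing eyes with it (at most 16 in the example above).
- A reader might infer that dropping any poor eye raises the Test rate. It does not if the eye is a Control eye. If failures were equally common in both arms, about one third of removals would have no effect.
- Eligibility is already narrow. Protocol 8.1 and 8.2 require a projected BCDVA better than 20/32 and exclude most corneal, macular and retinal pathology, which limits what a further clinically credible criterion could capture. The judgement item is confined to pre-operative pathology and is in the protocol too.
- Late exclusions would be visible. SAP 13.3.1 reports the same categories and tests for ITT and mITT, SAP 9.7 reports set counts and lists membership, SAP 13.5.2 lists eyes with BCDVA of 0.3 logMAR or worse, and Protocol 13.5.5.5 requires a subject-by-subject account of failures to reach 0.3 logMAR. Visibility lowers the risk but does not stop the test being decided on the altered set.
- The SAP states that it was finalized before any analyses. That dates the document. It does not close a clause which the document itself leaves open until unmasking.

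A reader might also infer that criteria were in fact added, or were chosen from acuity data. Nothing in the documents says so.

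**Conclusion.** The point holds as a gap in pre-specification. The definition of a required single-arm test stays open until treatment unmasking, and the only safeguard named, masking to arm, does not suit a test with no comparator arm.

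Its size depends on assumptions. The limit itself turns on one eye at each set size examined from 240 to 334. The gains in the chance of passing rest on 300 Test eyes and on true rates of 94% to 96%, and are upper bounds. They shrink or vanish when a criterion also removes many passing eyes. They are also small for a lens at or above 96.7%. The opening matters most for a lens a little below the standard, which is the case the test exists to detect.

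The documents do not support reading this as a threat to the whole BCDVA endpoint. The non-inferiority comparison and the 92.5% tests do not use this set, so the effect is confined to the third hypothesis, although that hypothesis is required for success. Confidence is high for the defect in the text and lower for its numerical effect.

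**What to change.** In SAP 8.5, delete "Prior to treatment unmasking, other criteria may be added". State that the Best Case criteria are those listed in Protocol 13.4.5 and SAP 8.5. Add that each first eye is classified before database lock, from the pre-operative record plus any finding of macular degeneration, by existing staff without access to post-operative acuity, with the reason listed per eye.

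If a criterion has already been added, let the test on the Protocol 13.4.5 definition decide success and report the expanded set as supportive.

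The cost is one deletion and a few sentences in the SAP, with no new data. The downside is that the definition can no longer be extended late.

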9.1 Unit of Analysis

The unit of analysis in this study will be the subject or the eyes for all efficacy and safety summaries.

9.2 Dropouts or Missing Data Handling

For primary analysis of primary and secondary effectiveness endpoints, missing data will not be imputed for the non-inferiority analyses and will be imputed using multiple imputation Markov Chain Monte Carlo (MCMC) methods for the superiority analyses (see [Section 13.3.2](#)). For analyses of safety and exploratory effectiveness endpoints, missing data will not be imputed unless specified otherwise.

Partial/missing start and end dates for AEs and concomitant medications will be imputed as follows:

Partial/missing start date:

- Dates with missing day only will be imputed as the 1st of the month unless the month and year are same as the month and year of the implant date for the corresponding eye for ocular AEs or the first implant date for the non-ocular AEs in which case missing day will be imputed as the implant day for the corresponding eye for ocular AEs or the first implant day for the non-ocular AEs.
- Dates with both day and month missing will be imputed as 1 Jan unless the year is same as the year of the implant date for the corresponding eye for ocular AEs or the first implant date for the non-ocular AEs, in which case missing day and month will be imputed as the implant day and month for the corresponding eye for ocular AEs or the first implant day and month for the non-ocular AEs.
- Completely missing dates will be imputed as the implant date for the corresponding eye for ocular AEs or the first implant date for the non-ocular AEs unless the end date is on or before the implant date for the corresponding eye for ocular AEs or the first implant date for the non-ocular AEs, in which case missing date will be imputed as 1 Jan of the same year as the end date.

Partial/missing end date for AEs reported as “Resolved:”

- Dates with missing day only will be imputed as the last day of the month.
- Dates with both day and month missing will be imputed as 31 Dec.
- Completely missing end dates will have an imputed end date of 31 Dec 2023
- If the imputed date is after the date of death, then the end date will be set equal to the date of death.

The original dates will be displayed in data listings and the imputed dates will be used in derivations only (study day, treatment-emergence status, etc.).

COVID-19-related missing data or visits will not be imputed for summaries and analyses but will be reported as protocol deviations and recorded in protocol deviation log.

9.3 Multicenter Issues

Data from all study centers will be combined for summaries/analyses, unless specified otherwise.

9.4 Multiplicity Issues

As all of the primary safety and effectiveness endpoints with success criteria described in [Section 3.3](#) are required to demonstrate statistical success, adjustment for multiplicity is not necessary for these endpoints.

Statistical testing of the secondary effectiveness endpoints with success criteria will not be evaluated for success unless all primary endpoints with success criteria are met. Primary and secondary endpoints without success criteria will not affect the evaluation of secondary endpoints with success criteria. The secondary effectiveness endpoint hypotheses will be evaluated hierarchically; therefore, adjustment for multiplicity is also not necessary for these endpoints.

Any statistical tests of endpoints that are not primary or secondary endpoints will be considered exploratory and will not be adjusted for multiplicity.

9.5 Visit Window

For analysis of data by visit, only in-window visit data will be included in the analysis of a scheduled visit's data. If a scheduled visit is completed outside of the prescribed visit window, then the visit and its window will be handled as follows:

- The out-of-window scheduled visit will be reclassified as an interim (unscheduled) visit.
- If one or more unscheduled visits occurred in the window, then the unscheduled visit that occurred closest to the center of the visit window will be reclassified as the in-window (scheduled) visit.
- If two unscheduled visits occurred in the visit window, are the closest visits to its center, and are equidistant from its center, then the later of the two visits will be reclassified as the in-window (scheduled) visit.

9.6 logMAR Calculation

The following effectiveness data will be assessed as letters read correctly (letters correct) or as count fingers (CF), hand motion (HM), light perception (LP), or no light perception (NLP):

- Photopic monocular/binocular UCDVA
- Photopic monocular/binocular BCDVA
- Photopic monocular/binocular UCNVA
- Photopic monocular/binocular DCNVA
- Mesopic monocular/binocular DCNVA
- Photopic monocular/binocular UCIVA
- Photopic monocular/binocular DCIVA
- Mesopic monocular/binocular DCIVA
- Binocular BCDVA Defocus Curves
- Photopic monocular BCDVA (simulated astigmatism)
- Photopic monocular DCNVA (simulated astigmatism)
- Photopic monocular DCIVA (simulated astigmatism)

The logMAR VA for the data listed above will be computed as follows for subjects who can read at least one letter.

$$\text{logMAR VA} = 1.70 - (0.02 \times \text{letters read correctly})$$

Subjects who cannot read any letters but who can count fingers will be assigned a logMAR VA value of 2.00. Subjects who cannot read any letters but who can perceive hand motion will be assigned a logMAR VA value of 2.30. Subjects who cannot perceive hand motion will be assigned a logMAR VA value of missing.

For UCDVA and BCDVA data, logMAR score will be captured in the Electronic Data Capture (EDC) database. The scores will not be pulled from EDC database directly.

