13.3.2 Photopic Monocular DCNVA

Phase I/Pilot subjects will be excluded from the analysis of this endpoint.

Photopic monocular DCNVA (logMAR) at 40 cm in first eyes at Post-Operative Visit 4 (Day 120 to 180 after second eye IOL implantation) will be summarized using continuous summary statistics in logMAR units by treatment assignment for the mITT Set.

If there are missing mITT Set monocular DCNVA data in first eyes at Post-Operative Visit 4 (Day 120 to 180 after second eye IOL implantation), then missing data will be imputed using the MCMC multiple imputation method. A total of 30 imputation datasets will be created. After imputation of missing data, the statistical hypotheses will be tested using an ANCOVA model with treatment and site as fixed factors by imputation.

SAS® code for the MCMC multiple imputation:

```
PROC MI DATA=indata OUT=mcmc NIMPUTE=30 SEED= 1091148178;  
  BY trt;  
  MCMC INITIAL=EM;  
  VAR V3 V4;  
  RUN;
```

where

- trt = treatment
- v3 = actual value at Visit 3A
- v4 = actual value at Post-Operative Visit 4 (Day 120 to 180 after second eye IOL implantation)

An overall p-value resulting from the multiple imputation method will be estimated. The treatment effect (LS mean for Test group IOL VA minus LS mean Control group IOL VA) in logMAR units and a two-sided 95% CI will be provided. If the p-value from the multiple imputation analysis is less than or equal to 0.05 and the treatment effect is less than or equal to -0.10 (i.e., the Test lens mean logMAR VA is at least 0.10 less than the mean for the control), then it will be concluded that the Test IOL is statistically and clinically successful (i.e., superior to the Control IOL) in this outcome.

The previous continuous summary statistics will also be provided for the PP Set. However, superiority will not be evaluated with the PP Set, and statistical success will not depend upon the results of the PP analysis.

As a sensitivity analysis, observed DCNVA (logMAR) at 40 cm in first eyes at Post-Operative Visit 4 (Day 120 to 180 after second eye IOL implantation) will be compared between treatment groups using an ANCOVA model with treatment and site as fixed factors. The treatment effect (LS mean for Test group IOL VA minus LS mean Control group IOL VA) in logMAR units and a two-sided 95% CI will be provided. The analysis will be for the ITT set.

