13.3.3 Photopic Monocular DCIVA

Phase I/Pilot subjects will be excluded from the analysis of this endpoint.

Photopic monocular DCIVA (logMAR) at 66 cm in first eyes at Post-Operative Visit 4 (Day 120 to 180 after second eye IOL implantation) will be summarized and analyzed similarly to the second primary effectiveness endpoint in [Section 13.3.2](#) using a seed of 1340584231 for multiple imputation.

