13.4 Secondary Effectiveness Analyses

13.4.1 Photopic Binocular DCNVA

Phase I/Pilot subjects will be excluded from the analysis of this endpoint.

Photopic binocular DCNVA (logMAR) at 40 cm at Post-Operative Visit 4 (Day 120 to 180 after second eye IOL implantation) will be analyzed using an ANCOVA with DCNVA as the dependent variable and treatment and site as fixed factors. The treatment effect (LS mean for Test group IOL minus LS mean for Control group IOL) will be estimated in addition to a two-sided 90% CI. The analysis will be based on observed data for ITT, mITT, and PP sets. Multiple imputation of missing data will not be applied.

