13.4.3 Photopic Binocular DCIVA

Phase I/Pilot subjects will be excluded from the analysis of this endpoint.

Photopic binocular DCIVA (logMAR) at 66 cm at Post-Operative Visit 4 (Day 120 to 180 after second eye IOL implantation) will be analyzed using an ANCOVA with DCIVA as the dependent variable and treatment and site as fixed factors. The treatment effect (LS mean for Test group IOL minus LS mean for Control group IOL) will be estimated in addition to a two-sided 90% CI. The analysis will be based on observed data for ITT, mITT, and PP sets. Multiple imputation of missing data will not be applied.

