13.5.2 Categorical Analysis of Visual Acuity

For all corrected and uncorrected visual acuity endpoints at Post-Operative Visit 4 (Day 120 to 180 after second eye IOL implantation), logMAR value will be converted to Snellen equivalent. Percentages of eyes that achieve VA in Snellen equivalent for each category in both mutually exclusive (20/10, 20/12.5, ..., 20/200, worse than 20/100) and cumulative categories (20/200 or better, 20/160 or better, ..., 20/12.5 or better) for first eyes, second eyes, and all eyes will be summarized by treatment group.

Categorical summaries will use the logMAR to Snellen conversion values as shown in Table 5.

Table 5. logMAR to Snellen Equivalent Conversion

logMAR Value, Rounded to the Nearest 0.1	Snellen Equivalent
Missing	Missing
-0.3	20/10
-0.2	20/12.5
-0.1	20/16
0.0	20/20
0.1	20/25
0.2	20/32
0.3	20/40
0.4	20/50
0.5	20/63
0.6	20/80
0.7	20/100
0.8	20/125
0.9	20/160
1.0	20/200
> 1.0	Worse than 20/200

The following rates will be also provided by treatment randomized for the mITT set; and for first eyes, second eyes, and all eyes where applicable:

- Rate of loss of visual acuity of 0.2 logMAR or more from Preoperative Visit 0A/B (Day -30 to -5) to post-operative Visit 4 in UCDVA
- Rates of loss of visual acuity of 0.2 logMAR or more from Preoperative Visit 0A/B (Day -30 to -5) to post-operative Visit 4 in BDCVA

Visual acuity data will be presented in a data listing. In addition, BCDVA of ≥ 0.3 logMAR and visual acuity data with a loss of at least 0.2 logMAR in UCDVA and BDCVA will be presented separately in data listings.

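### SAP 9.6 sets recorded light perception and no light perception to missing, so a known worst outcome leaves the BCDVA non-inferiority analysis and is imputed for primary DCNVA and DCIVA (minor; small expected effect)

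*SAP*

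**What the plan says.** SAP 9.6 (logMAR Calculation) allows acuity to be recorded as letters read, count fingers, hand motion, LP or NLP. Letters go through the usual formula, count fingers becomes 2.00 and hand motion 2.30. For anything worse: "Subjects who cannot perceive hand motion will be assigned a logMAR VA value of missing".

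What then happens to a missing first-eye value at Visit 4 depends on the endpoint:

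- **BCDVA non-inferiority.** SAP 9.2: "missing data will not be imputed for the non-inferiority analyses". SAP 13.3.1 repeats it: "Therefore, missing data will not be imputed for the BCDVA non-inferiority test".
- **Primary monocular DCNVA.** SAP 13.3.2: "then missing data will be imputed using the MCMC multiple imputation method". The code runs by treatment and uses only the Visit 3A and Visit 4 values. The sensitivity analysis uses observed values. Phase I/Pilot subjects are outside this test.
- **Primary monocular DCIVA.** SAP 13.3.3: this endpoint "will be summarized and analyzed similarly to the second primary effectiveness endpoint".
- **Categorical acuity.** SAP 13.5.2, Table 5, maps a missing logMAR value to a Missing row, although the table also has a row for acuity worse than 20/200. The same section says that "visual acuity data with a loss of at least 0.2 logMAR in UCDVA and BDCVA will be presented separately in data listings".

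Protocol 13.5.3.1 gives only the letter formula, and SAP section 16 does not list the coding among the changes from the protocol.

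**The concern.** LP and NLP are results, not absent measurements. Under this rule an eye at hand motion carries the worst score in the dataset, and the same eye one step worse carries none. The eye leaves the BCDVA mean comparison. In the DCNVA and DCIVA comparisons, an eye that lost vision after Visit 3A receives a value predicted from the acuity it had before the loss. The observed-data sensitivity analysis for those endpoints does not repair this, because it omits the eye as well.

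These three comparisons decide trial success. On each of them, removing a known failure flatters the arm in which it occurred. Table 5 also understates the worst category, and the 0.2 logMAR loss rate and listing cannot pick up an eye with no logMAR value.

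**Working it through.** **Inputs.** From SAP 6.4: 300 Test and 150 Control eyes for BCDVA, expected difference 0.00, SD 0.15; 276 and 138 for DCNVA and DCIVA. Margin 0.10 and two-sided 90% interval from SAP 13.3.1. Assumed: LP/NLP scored at v = 2.30 (the SAP's own hand-motion value), site ignored, such eyes in the Test arm only.

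**Plan's own figures.** SE = 0.15 × √(1/300 + 1/150) = 0.0150. Power = Φ(0.10/0.0150 − 1.645) = Φ(5.02) > 0.999, consistent with the stated 99%. For the -0.10 clinical threshold at a true difference of -0.12: SE = 0.15 × √(1/276 + 1/138) = 0.0156 and Φ(0.02/0.0156) = 90%, against the stated 89%.

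**BCDVA limit with k Test eyes scored 2.30.** Let the other Test eyes have mean d and the Control eyes mean 0.

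- Test mean: m = [(300 − k)d + kv]/300
- Pooled variance: s² = [(299 − k)0.15² + (300 − k)(d − m)² + k(v − m)² + 149 × 0.15²]/448
- Upper limit: m + 1.648 × s × √(1/300 + 1/150) = m + 0.1648s

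With d = 0:

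| k | m | Test SD | s | Upper limit |
|---|---|---|---|---|
| 0 | 0 | 0.150 | 0.150 | 0.025 |
| 1 | 0.0077 | 0.200 | 0.185 | 0.038 |
| 3 | 0.0230 | 0.274 | 0.240 | 0.063 |
| 6 | 0.0460 | 0.355 | 0.303 | 0.096 |
| 7 | 0.0537 | 0.378 | 0.321 | 0.107 |

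With one such eye removed, as the SAP now has it, the limit is 0.025. If v = 3.0 is assumed instead, five eyes cross the margin (0.107).

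**When the coding decides the result.** With k eyes, removal and scoring disagree only if the remaining Test eyes are observed worse than Control by an amount inside a band: 0.062 to 0.075 for k = 1, 0.050 to 0.075 for k = 2, 0.038 to 0.075 for k = 3. For example, at d = 0.07 with one eye, the limit is 0.095 removed and 0.108 scored.

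**Combined probability.** Sum over k ≥ 1 of P(K = k) × P(observed difference in band k), with K binomial(300, r) and the difference normal with SE 0.15 × √(1/(300 − k) + 1/150). No rate r is given in the documents; 0.1% and 0.4% are illustrations. The larger is the sum of the endophthalmitis (0.1%) and retinal detachment (0.3%) rates in SAP Table 2.

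| r | True difference 0 | True difference 0.05 |
|---|---|---|
| 0.1% | 0.005% | 5% |
| 0.4% | 0.3% | 25% |

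For the last cell, k = 1, 2, 3 contribute 0.362 × 0.159 + 0.217 × 0.451 + 0.087 × 0.736 = 0.22, and larger k the remainder.

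**DCNVA and DCIVA.** If an eye is imputed near an assumed Test mean of 0.20, scoring it 2.30 instead shifts the Test mean by (2.30 − 0.20)/276 = 0.0076. At a true difference of -0.12, one such eye lowers the chance of observing at least -0.10 from 90% to Φ((0.02 − 0.0076)/0.0156) = 79%.

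**The case against.** The strongest case against is that this rarely matters. The rule treats both arms alike. Eligibility excludes much of the relevant pathology and requires projected BCDVA better than 20/32, so few such eyes should occur. At the planned zero difference the chance of a changed conclusion is a fraction of one per cent. The loss would still be visible as an adverse event (Protocol 12.4.1), in the acuity listings, and under the separate rule for losses of 10 letters or more (SAP 3.2.6, Protocol 13.5.5.5), which works in letters and can identify an eye that reads none. Any score for LP or NLP is also partly arbitrary: 2.30 lies about 15 planned SDs from a mean of zero (2.30/0.15). All of this stands and sets the priority. None of it returns the eye to the primary comparisons.

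Three stronger readings are tempting, and the documents do not support them.

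- *The 20/40 tests lose failed Test eyes.* SAP 13.3.1 gives no denominator of its own, but the default in SAP section 7 is the analysis population unless stated otherwise. That keeps the eye in as a non-success. Examples in which one dropped eye reverses these tests require setting that default aside and, for the 96.7% test, assuming 300 Best Case eyes.
- *0.4% is an upper bound on the event rate.* Benchmark rates do not cap what can occur, other causes exist, and the rates are cumulative rather than the share at LP or NLP at Visit 4.
- *Eyes too poor to refract disappear by a second route.* Protocol Appendix B 1.1 says BCDVA is not tested when refraction cannot be obtained, but that is the preoperative section. Section 1.2 carries over the refraction method without stating that consequence. This merits a clarification only.

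The binocular secondary analyses on observed data would also omit such a result, but that normally needs both eyes to be this poor.

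**Conclusion.** The point holds as a minor one. The SAP contains an explicit rule that turns a recorded worst outcome into a missing value, and no other section restores it to the BCDVA, DCNVA or DCIVA comparisons. A reader might infer that non-inferiority is in serious doubt, or that the rule systematically favours the Test lens. Neither follows: seven Test eyes at an assumed 2.30 are needed to cross the margin at equal means, and the direction depends on the arm in which the event occurs. The coding becomes material only if the true BCDVA difference is already around half the margin. The sizes rest on an assumed score, illustrative event rates, the planned SD of 0.15 and no such eye in the Control arm. The coding rule itself can be read directly from the text.

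**What to change.** - **SAP 9.6:** treat recorded LP and NLP as observed results. Reserve missing for acuity that was not assessed.
- **Means:** before unmasking, prespecify a value no better than the SAP's hand-motion value of 2.30, with a worse value as a sensitivity analysis. The documents give no LP/NLP score, so the sponsor must choose and state it.
- **SAP 13.3.2 and 13.3.3:** keep these eyes out of the multiple imputation.
- **SAP 13.3.1 and Table 5:** count them as worse than 20/40, confirm that they stay in the 20/40 denominator as failures (consistent with section 7), and tabulate them as worse than 20/200.
- **Optional clarification:** say how a postoperative acuity recorded as not done because refraction could not be obtained is handled. The protocol already requires the reason in the source document and eCRF.

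The cost is a few sentences and no new data collection. The downside is borne only if such an eye occurs: one Test eye at 2.30 raises the Test SD from 0.15 to 0.20 and the upper limit as shown above, and the result then depends in part on the chosen score. That is why the score should be fixed in advance and varied in a sensitivity analysis.
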